437 The prevalence surveys are conducted independently from the offer of opportunistic chlamydia
438 testing by GPs. A research assistant employed by the research team will be based in each clinic to
439 recruit patients for the prevalence survey. About 80 patients per cluster area will be recruited (see
440 sample size calculation); the number of patients per clinic will be proportionately allocated across all
441 clinics in the cluster according to the number of 16 to 29 year olds on the clinic files. Consecutive
442 patients will be approached to minimise selection bias. The research assistant will approach patients
443 in the clinic waiting room and determine eligibility (patient age, whether they have ever had vaginal
444 or anal sex). If the individual meets the eligibility criteria, they will be invited to participate in the

445 study and signed informed consent will be obtained. Basic data (age, gender and ever had sex) will
446 be collected from all patients to determine the response rate and assess non-response bias. It is not
447 logistically feasible to estimate the population prevalence of chlamydia from cross-sectional surveys
448 of representative samples of the whole target population in each cluster. It is likely that chlamydia
449 positivity measured in clinic attenders is higher than true population prevalence but it is a valid
450 proxy under the following conditions: the participation rate is high enough to minimise selection
451 bias, the response rate at the end of the intervention period is similar to the baseline response rate
452 and the characteristics of clinic attenders do not change systematically during the intervention
453 period. Baseline prevalence in clinic attenders will be estimated prior to cluster randomisation, so
454 should be balanced in intervention and control clusters.

455 ***Secondary endpoints***

456 **Pelvic inflammatory disease (PID)**

457 The cumulative incidence of PID due to any cause in the intervention and control groups will be
458 measured; the numerator is the number of cases of PID diagnosed during the intervention period
459 among women aged 16–34 years attending participating clinics. The denominator will be the
460 number of female patients aged 16–34 years with at least one consultation at the clinic during the
461 intervention period. The upper age limit will allow diagnoses to be included from women aged 25 to
462 29 years at enrolment, who develop PID some years after chlamydia infection.

463 To help reduce measurement bias, GPs in both intervention and control clusters will be provided
464 with the same PID diagnosis and management education pack which has been accredited by both
465 the Royal Australian College of General Practitioners and the Australian College of Rural and Remote
466 Medicine. GPs are advised to diagnose PID according to the clinical criteria of the Centers for Disease
467 Control and Prevention, which recommend treatment when any one of the following signs are
468 present: uterine tenderness, adnexal tenderness or cervical motion tenderness in sexually active
469 young women at risk of STIs where no other cause is identified [28]. Clinical diagnostic criteria have
470 been shown to have sensitivity and specificity of 87% and 50%, respectively in hospital settings [86].
471 It is acknowledged that ascertainment bias in the diagnosis of PID by GPs cannot be eliminated
472 because their clinical judgment can be influenced by knowledge of a woman's chlamydia test status.

473 GPs will be advised to record PID diagnoses in their electronic medical records via drop-down lists
474 and pre-coded lists where available, in preference to recording the diagnoses as uncoded free text.
475 STI test results associated with the PID diagnosis will be extracted and linked with the PID diagnosis.

476 The number of hospital admissions or emergency department attendance associated with PID (on
477 the basis of ICD 10 codes) will be obtained from each State health department. Hospitalisation data
478 will include the age and residential postcode for each patient. Any GP referral for PID to a hospital
479 will be collected.

480 **Epididymitis**

481 The cumulative incidence of epididymitis due to any cause in the intervention and control groups
482 will be measured; the numerator is the number of diagnoses of epididymitis during the trial period
483 among men aged 16 to 29 years. The denominator will be the number of male patients aged 16 to
484 29 years with at least one consultation at the clinic during the trial period. The diagnosis of
485 epididymitis will be based on clinical symptoms, as described by Trojian and Lishnak [26]. In order to
486 minimise measurement bias, GPs in the intervention and control groups will be provided with
487 information on the diagnosis of epididymitis and will be requested to use consistent clinical
488 reporting text in the medical records. STI test results associated with the epididymitis diagnosis will
489 be extracted and linked with the epididymitis diagnosis.

490 **Testing uptake rates**

491 Testing uptake per year (with 95% CI) of eligible patients will be assessed in intervention and control
492 groups as an overall measure, as well as stratified by sex, age group (16 to 19, 20 to 24, 25 to 29
493 years) and Aboriginal and/or Torres Strait Islander status. The numerator will be the number of
494 individuals aged 16 to 29 years who were tested for chlamydia at least once in the past year; the
495 denominator will be the number of unique individuals aged 16 to 29 years who had a consultation
496 with a GP at the clinic in the past year. The denominator will include patients who have not had
497 sexual intercourse, as this information is not recorded on patient records. The Australian Study of
498 Health and Relationships [87] or similar up-to-date data will be used to adjust denominators for the
499 proportion likely to be sexually active.

500 **Annual re-testing rate**

501 Overall annual re-testing of eligible patients will be determined in intervention and control clusters,
502 and stratified by sex, age group (16 to 19, 20 to 24, 25 to 29 years) and Aboriginal and/or Torres
503 Strait Islander status. The numerator will be the number of individuals aged 16 to 29 years who were
504 tested for chlamydia 12 months (allowable range 10 to 15 months) after a previous chlamydia test;
505 the denominator will be the number of unique individuals aged 16 to 29 years who had at least one

506 chlamydia test in the previous year. The Australian Study of Health and Relationships [87] or similar
507 up-to-date data will be used to adjust denominators for the proportion likely to be sexually active.

508 **Test for repeat infection**

509 Tests for repeat infection in eligible patients following a positive chlamydia diagnosis will be
510 measured overall in intervention and control clusters, and stratified by sex, age group (16 to 19, 20
511 to 24, 25 to 29 years) and Aboriginal and/or Torres Strait Islander status. The numerator will be the
512 number of individuals aged 16 to 29 years re-tested for chlamydia three months (allowable range six
513 weeks to six months) after a positive test; the denominator will be the number of unique individuals
514 aged 16 to 29 years who tested positive for chlamydia in the previous year.

515 **Repeat infection rates**

516 Repeat infection rates in eligible patients in intervention clusters only will be assessed as the number
517 of people with a positive repeat chlamydia test taken from 6 weeks to 6 months after an initial
518 positive test, as a proportion of all chlamydia positives at the initial visit. It will not be possible to
519 distinguish re-infection from an untreated partner from persistent infection following treatment
520 failure or acquisition of infection from a new partner, because samples tested in routine diagnostic
521 laboratories are not retained for genotyping.

522 ***Data collection***

523 ***GP characteristics***

524 GP characteristics will be collected via questionnaires and analysis of clinic consultation data prior to
525 commencement of the trial and will include demographics (age, sex, years worked as a GP);
526 education details (country of qualification, postgraduate qualifications); and knowledge, awareness,
527 attitudes and practices with respect to chlamydia testing and management. GPs' partner notification
528 practices and their familiarity with the clinical diagnostic features of PID will be assessed in the
529 questionnaire.

530 ***Patient characteristics***

531 Data from patients taking part in baseline and final prevalence surveys will be collected by self-
532 completed questionnaire using handheld computers. Data items include demographics (age, sex,
533 Aboriginal and/or Torres Strait Islander status, ethnic/cultural background, postcode of residence);
534 sexual behaviour data (proportion currently in a sexual relationship, number of sexual partners by
535 sex within last 3 and 12 months, number of new sexual partners in the last 12 months, duration of

536 most recent sexual partner, any concurrent or overlapping partnerships); presence of any symptoms
537 associated with chlamydia; and history of past chlamydia testing. The postcode of residence of
538 sexual partners will not be collected.

539 Minimal data including age, gender and whether ever had sex will be collected from all patients who
540 refuse to participate in the prevalence survey. These data will be used to assess non-response bias.

541 ***Chlamydia testing, diagnosis and sequelae data***

542 A data extraction tool (GRHANITE™, licensed by the University of Melbourne; www.grhanite.com)
543 will be installed on clinic computers where possible. This data extraction tool will provide ongoing
544 collection of consultation and chlamydia testing data, with patients de-identified but including a
545 unique identification code. As a backup, consent will also be obtained to collect quarterly chlamydia
546 testing numbers from each clinic's pathology provider, and from Medicare Australia, the Australian
547 Government Insurance Scheme that funds chlamydia general practice consultations and chlamydia
548 tests in Australia. The data obtained via the pathology provider or Medicare will not include a unique
549 identification code. The data collected will include chlamydia testing rates for the 12 months prior to
550 trial commencement; chlamydia positivity rates for the 12 months prior to trial commencement,
551 and; number of PID and epididymitis diagnoses for the 12 month prior to trial commencement.
552 During the trial, the data collected will include the number of consultations with 16–29 year olds;
553 the number of chlamydia tests for 16–29 year olds; the number of repeat tests for 16 to 29 year
554 olds; the number of 16–29 year olds testing positive for chlamydia and re-testing following testing
555 positive; the number of PID cases diagnosed among women aged 16–34 years at participating GP
556 clinics and local hospitals; and the number of epididymitis cases diagnosed among men aged 16–29
557 years at participating GP clinics and local hospitals. The number of cases of PID and epididymitis
558 associated with chlamydia will be reported where a laboratory test has been done and the number
559 of PID cases referred to a hospital will also be extracted. The automated data extraction tool
560 provides data from clinics in intervention and control areas in a way that cannot be subverted. This
561 will help to minimise bias in the measurement of chlamydia test uptake and re-testing rates.

562 ***Adverse-events reporting***

563 Patients receiving the intervention could experience adverse events after receiving a diagnosis of
564 chlamydia or from antibiotic treatment. Levels of anxiety and of partnership breakdown in women
565 screened for chlamydia in the USA have been reported to be more common in those receiving a

566 positive than a negative test result [88]. Azithromycin can cause minor gastrointestinal upset, but
567 rarely causes serious side effects [84, 89].

568 During the intervention period passive surveillance for adverse events will be undertaken. The
569 overall numbers of events in intervention and control clinics will be reported. Diagnoses of anxiety
570 and referrals for psychological or psychiatric treatment will be extracted from the clinics' electronic
571 medical records where possible. However, it will not be possible to assess causality from these data.
572 In the final prevalence survey, the questionnaire administered to patients attending both
573 intervention and control clinics will ask them to report whether they experienced any anxiety or
574 issues with their partner following any chlamydia test they had during the intervention period and
575 whether their chlamydia test result was positive or negative. These data will also be reported.

576 ***Statistical analysis plan***

577 ***Sample size and power calculations***

578 Table 1 summarises the total numbers of randomised clusters required to detect differences in
579 estimated chlamydia prevalence (the primary outcome measure) between intervention and control
580 arms at the end of the trial. The calculations were based on the following assumptions:

- 581 1. The intra-class correlation coefficient (ICC) was estimated from individual practice data to be
582 0.009 [90]. Since combining practices into clusters in the trial design is likely to reduce the ICC,
583 calculations were also performed using ICC = 0.007 and ICC = 0.005.
- 584 2. The design effect (the inflation of the sample size to allow for between area variability) was
585 calculated as $1 + (n - 1) * ICC$, where n is the number of people tested at each area.
- 586 3. All calculations are for 80% power and use a two-sided significance level of 5% [61].

587 Table 1 shows that 54 clusters (27 in each group) are required to detect a difference in chlamydia
588 prevalence between the intervention and control groups of 2% at the end of the trial with 80%
589 power (4% in control and 2% in intervention group). Within each of the geographical areas, 80 men
590 and women aged 16 to 29 years will be tested for chlamydia during each prevalence survey.
591 Statistical power will be increased if a higher than expected chlamydia prevalence is obtained at
592 baseline or if the ICC is lower than estimated. If the ICC is found to be 0.005, 54 clusters will give 89%
593 to detect a difference of 2% at the end of the trial.

594 ***Baseline data***

595 Cluster, clinic and participant baseline characteristics will be summarised by randomised group as
596 appropriate. There will be no statistical hypothesis tests for this comparison.

597 ***Type of analysis***

598 Primary analyses of the trial endpoint will be according to the intention to treat principle, with
599 clusters analysed according to their randomised group, regardless of the level of uptake of the
600 intervention. Secondary analyses of the measurement outcomes will explore the effect of adherence
601 to the intervention, first by excluding clusters with poor adherence, and second by regression of
602 measures of cluster adherence on outcomes.

603 ***Statistical tests***

604 Formal statistical comparisons will be based on generalised mixed models that can account for
605 cluster, clinic and participant variability. Generalised estimating equation (GEE) approaches, with
606 robust standard errors, will be adopted using STATA statistical software (StataCorp, College Station,
607 TX, USA). Initial analyses will be simple, unadjusted comparisons of randomised areas. If there
608 appear to be any important imbalances between randomised groups in terms of baseline covariates,
609 adjusted analyses will also be performed, and presented in addition to unadjusted comparisons. The
610 impact of other potential confounding factors such as age and gender of the patients and GPs, and
611 socio-economic profile of the area served by the clinic will also be investigated in this analysis. The
612 difference between intervention and control clusters will be estimated, with 95% confidence
613 intervals and p-values from the corresponding hypothesis tests. Statistical significance will be taken
614 as a two-sided p-value less than 0.05, with no adjustment for multiple comparisons.

615 Outcome measures will be assessed as follows:

- 616 • Chlamydia prevalence in clinic attenders after the intervention period will be summarised by
617 randomised group, and by sex and age group. Formal comparisons will be based on
618 hierarchical logistic regression models.
- 619 • Incidence of PID per 100 female patients seen at a clinic will be summarised by randomised
620 group and by age group. Analyses will be based on Poisson regression models.
- 621 • Incidence of epididymitis per 100 male patients seen at a clinic will be summarised by
622 randomised group and by age group. Analyses will be based on Poisson regression models.

- 623 • Testing uptake rates, testing coverage, annual re-testing rates, testing for reinfection and
624 rates of re-infection will be summarised by randomised group and compared using
625 appropriate hierarchical models.

626 ***Planned subgroup analyses***

627 The effect of the intervention within different subgroups of clusters will be explored, but interpreted
628 cautiously given the relatively small number of clusters. Subgroups may include sex, age group, area
629 type, Aboriginal and/or Torres Strait Islander status, estimated baseline chlamydia prevalence and
630 baseline testing rate. Intervention and control clusters will be compared within each subgroup and
631 evidence for heterogeneity of effects assessed using tests for interaction between randomised
632 intervention and subgroup. The effect of GP and clinic characteristics on testing uptake, annual
633 retesting rates, retesting after a positive diagnosis and chlamydia prevalence will be investigated.
634 The impact of patients attending from an area outside of the cluster will be investigated by analysing
635 patient postcode and its association with chlamydia prevalence.

636 ***Ethical issues***

637 ***Ethics committee approval***

638 The ACCEPt trial has been approved by the RACGP National Research and Evaluation Ethics
639 Committee and the University of Melbourne Human Research Ethics Committee. Approval has also
640 been obtained from the Aboriginal Health and Medical Research Council (AHMRC) Ethics Committee
641 to conduct the ACCEPt trial in AMSs. Specific services may also request ethical approval be sought
642 from local ethical committees.

643 ***Informed consent and information sheets***

644 ACCEPt research staff will explain the data collection requirements of the trial to all clinic staff prior
645 to them providing informed consent. Informed consent will cover all data collection activities of the
646 trial, recognise the principles of confidentiality and data ownership and define processes for
647 reporting of findings and release of trial results. A plain language participant information sheet will
648 be provided, which summarises the trial, participation requirements, confidentiality and disclosure
649 of information, and ethics approval and complaints contacts.

650 GPs can withdraw from the trial by notifying ACCEPt staff at any time and completing a withdrawal
651 of informed consent form. Unless otherwise requested, data collected from the clinic up until the
652 time of withdrawal will be included in the analysis of the trial. Practice nurse participation will also

653 require informed consent. A plain language information sheet will be provided and withdrawal at
654 any time is possible with a withdrawal of informed consent form.

655 For the prevalence surveys, ACCEPt staff will explain prevalence survey participation to patients
656 attending clinics for consultations with a GP. Informed consent will cover the provision of chlamydia
657 test results to ACCEPt, and confidentiality of the test results and questionnaire responses. Plain
658 language participant information sheets for females and males will be provided, summarising the
659 trial, the requirements of participation in the prevalence survey, confidentiality and disclosure of
660 information, and ethics approval and complaints contacts. Patients may withdrawal at any time with
661 a withdrawal of informed consent form.

662 ***Interim analyses and stopping rules***

663 There will be no interim analyses of the primary endpoint, and no formal stopping rules adopted.

664 ***Data monitoring committee***

665 No independent data-monitoring committee has been appointed. An advisory committee has been
666 appointed to give advice about the intervention and its implementation in general practice clinics
667 and AMSs. The advisory committee is comprised of representatives from general practice, including
668 GPs, practice nurses and practice managers; a pathology provider; the National Aboriginal
669 Community Controlled Health Organisation (NACCHO); a youth advocacy group; and a rural sexual
670 health researcher.

671 ***Indemnities***

672 The trial is covered by the University of Melbourne's Professional Indemnity Insurance Policy (Vero
673 Profin, Melbourne), General and Product Liability Policy (Unimutual Limited, Sydney). The University
674 of Melbourne is also a WorkSafe Victoria approved self-insurer for workers' compensations.

675 ***Publication plan***

676 The trial results will be submitted to peer-reviewed journals for publication and presented at
677 national and international conferences. Results for chlamydia prevalence, PID and epididymitis
678 incidence, and chlamydia testing rates will be published separately. Results obtained through the
679 pre-trial prevalence survey will also be submitted for publication.

680 ***Reporting***

681 Reporting of the trial will be in accordance with the Consolidated Standards for Reporting Trials
682 extension to cluster randomised trials (CONSORT statement) [87]. These standards ensure the
683 complete and transparent reporting of a core set of components of the design and conduct of a
684 randomised controlled trial.

685 ***Trial registration***

686 The trial has been registered with the Australian Clinical Trial Register. (<http://www.anzctr.org.au>)-
687 number ACTRN12610000297022.

688 ***Funder***

689 Funding has been obtained from the following sources:

- 690 • Australian Government Department of Health and Ageing, request for tender for the Design,
691 Modelling and Evaluation of the Chlamydia Pilot in General Practice (RFT 266/0607).
- 692 • Australian National Health and Medical Research Council, grant numbers APP1007937 and
693 APP1056803.
- 694 • Victorian Department of Health.

695 ***Start date***

- 696 • Date trial started: July 2010

697 ***Finishing date***

- 698 • Expected end date: December 2015

699 ***Reporting date***

- 700 • Expected reporting date: June 2016

701 ***Acknowledgements***

702 This protocol is submitted on behalf of the ACCEPt Consortium of investigators: [name],
703 [name], [name], [name], [name], [name], [name], [name],
704 [name], [name], [name], [name], [name], [name], [name]
705 [name], [name], [name], [name], [name], [name], [name], [name]

706 [name] and [name]. Thank you to [name], University of Melbourne, who helped with
707 drafting the protocol and responding to reviewers' comments.

708

709 **References**

[figure not shown]
- 710 1. The Kirby Institute, *HIV, viral hepatitis and sexually transmissible infections in Australia:*
711 *Annual Surveillance Report 2012*. 2012, University of New South Wales: Sydney.
- 712 2. Health Protection Agency. *Genital Chlamydia trachomatis ('chlamydia')*. 2012 [cited 2012
713 October 2]; Available from:
714 <http://www.hpa.org.uk/Topics/InfectiousDiseases/InfectionsAZ/Chlamydia/>.
- 715 3. Centers for Disease Control and Prevention, *Sexually transmitted disease surveillance 2011*.
716 2012, Department of Health and Human Services: Atlanta, U.S.A.
- 717 4. Australian Government Department of Health and Ageing. *National Notifiable Diseases*
718 *Surveillance System*. 2011.
- 719 5. Hocking, J., et al., *A chlamydia prevalence survey of young women living in Melbourne,*

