238 The main research centres involved in the study are:

- 239 • Melbourne School of Population Health, University of Melbourne (managing institution)
- 240 • Kirby Institute, University of New South Wales
- 241 • Department of General Practice, University of Melbourne
- 242 • Institute of Social and Preventive Medicine, University of Bern

243 ***Contact details***

244 Associate [name]
245 Melbourne School of Population Health
246 University of Melbourne
247 [name]
248 [name]
249 [contact]
250 Email: [contact]

251 ***Aims and Objectives***

252 The study is a trial of the effectiveness of an intensive multifaceted intervention to increase rates of
253 annual chlamydia testing in primary care clinics (general practice clinics and AMSs). The hypothesis is
254 that by increasing testing rates to 30% of men and women aged 16 to 29 years, prevalence in clinic

255 attenders will decrease from about 4% to 2% in this population by the end of the trial period by the
256 end of the trial period.

257 ***Primary objective***

- 258 ● To determine whether an intervention to deliver organised regular chlamydia testing for
259 women and men aged 16 to 29 years who have ever had sex attending primary care clinics
260 (general practices and AMSs) leads to a reduction in estimated chlamydia prevalence in 16–
261 29-year old primary care attendees when compared with usual care.

262 ***Secondary objectives***

- 263 ● To determine whether an intervention to deliver organised regular chlamydia testing in
264 primary care clinics (general practices and AMSs) leads to a reduction in the incidence of PID
265 in 16–29-year old primary care attendees.
- 266 ● To determine whether an intervention to deliver organised regular chlamydia testing in
267 primary care clinics (general practices and AMSs) leads to a reduction in the incidence of
268 epididymitis in 16–29-year old primary care attendees.
- 269 ● To determine whether an intervention to deliver organised regular chlamydia testing in
270 primary care clinics (general practices and AMSs) can increase chlamydia testing rates.
- 271 ● To determine the proportion of individuals tested who return for a repeat test 12 months
272 after a previous negative test result.
- 273 ● To determine the proportion of individuals tested who return for a repeat test three months
274 after a positive chlamydia test result.

275 ***Design***

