301 There are inclusion and exclusion criteria at the level of the cluster, the primary care clinic,
302 healthcare professionals and individual patients.

303 ***Clusters***

304 **Inclusion criteria**

- 305 • Rural areas (postcodes) in the Australian States of New South Wales, Victoria, Queensland
306 and South Australia.
- 307 • A minimum population size of five hundred 15 to 29 year olds, as determined by the 2006
308 census data from the Australian Bureau of Statistics.
- 309 • Up to six general practice clinics.

310 **Exclusion criteria**

- 311 • Postcodes with army bases, mining towns, holiday towns or towns with intensive chlamydia
312 control activities.
- 313 • Postcodes with seven or more general practice clinics.
- 314 • Postcodes where one or more clinics refuse to participate in the trial.

315 ***General practice clinics and Aboriginal Medical Services (AMSs)***

316 All general practice clinics and AMSs (irrespective of size) within a cluster will be invited to
317 participate.

318 **Inclusion criteria**

- 319 • Over 75% of GPs working at the clinic must consent to participate in the trial.

320 **Exclusion criteria**

- 321 • None.

322 ***General practitioners and practice nurses***

323 General practitioners (GPs) and practice nurses (PNs) in clinics within eligible clusters will be invited
324 to participate. Consenting GPs and PNs will be recruited prior to the baseline prevalence survey, and
325 newly employed GPs and PNs at participating clinics will be recruited during the trial.

326 **Inclusion criteria**

- 327 • GPs and PNs (fully qualified, locum, and in training) working at participating general practice
328 clinics or AMSs.

329 **Exclusion criteria**

- 330 • None.

331 ***Individuals during the intervention period***

332 GPs will assess the eligibility of patients for chlamydia testing during a clinical consultation.

333 **Inclusion criteria**

- 334 • Men and women aged 16 to 29 years of age who have ever had vaginal or anal sex will be
335 targeted for annual chlamydia testing when they attend a participating clinic for any reason
336 during the trial.

337 **Exclusion criteria**

- 338 • None

339 ***Individuals enrolled in the baseline and final prevalence survey***

340 Research staff will assess eligibility.

341 **Inclusion criteria**

- 342 • Male and female patients aged 16–29 years attending a clinic for consultation with a GP.
343 • Ever had vaginal or anal sexual intercourse.

344 **Exclusion criteria**

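### The PID endpoint counts all women aged 16–34, although the objective and the testing target stop at 29 and the stated reason does not cover women already 30–34 at the start

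*Protocol*

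**What the plan says.** Four parts of the Protocol set an age range that bears on PID.

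- **Secondary objectives:** the question is whether the intervention "leads to a reduction in the incidence of PID" "in 16–29-year old primary care attendees".
- **Individuals during the intervention period, inclusion criteria:** "Men and women aged 16 to 29 years of age who have ever had vaginal or anal sex will be" targeted for annual testing.
- **Secondary endpoints, Pelvic inflammatory disease (PID):** cases are counted "among women aged 16–34 years attending participating clinics". The denominator is the "number of female patients aged 16–34 years with at least one consultation at the clinic during the" intervention period. The reason given is: "The upper age limit will allow diagnoses to be included from women aged 25 to" "29 years at enrolment, who develop PID some years after chlamydia infection".
- **Chlamydia testing, diagnosis and sequelae data:** "the data collected will include the number of consultations with 16–29 year olds". The same list takes PID cases in women up to age 34.

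The intervention runs for up to four annual rounds. Under Statistical tests, PID incidence per 100 female patients is summarised by arm and age group and analysed by Poisson regression. Epididymitis, by contrast, uses 16–29 in its objective, its endpoint and the data list.

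**The concern.** The extension to 34 is deliberate, and its purpose is sound: a woman aged 29 at the start can develop PID from an earlier infection after she turns 30. The rule as written does more than that. It sets no condition on age at the start or on ever having been in the target age group. Apart from the prevalence surveys, patients are not individually enrolled, so an age at enrolment cannot do the filtering for PID. Every attender aged 30–34 on the first day enters both numerator and denominator, though the intervention never targeted her.

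Two things are at stake. The endpoint does not measure what the objective asks. And adding women with little or no expected effect should pull the rate ratio toward 1 for an uncommon outcome on which the trials cited in the Background were imprecise. PID is the first secondary objective, and preventing it is one of the two goals of screening that the Protocol names.

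**Working it through.** The Protocol gives no sample size for PID, so there is no planned figure to reproduce. The 54 clusters are for chlamydia prevalence and are not affected.

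**Inputs from the Protocol:** endpoint ages 16–34 (19 single years of age); target ages 16–29 (14 years); intervention up to 4 years. For the effect, take the 35% reduction that the Background reports for the individually randomised London trial, as an illustration.

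**Assumptions, not in the Protocol:** ages spread evenly, equal attendance at all ages, the full four years, and at first a flat PID rate and no benefit to women never eligible.

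**Step 1, does the limit fit its reason?** A woman just under 30 at the start is just under 34 after four years. The limit of 34 therefore keeps every woman the reason describes.

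**Step 2, share of never-eligible women.** At time *t* years they occupy ages 30 + *t* up to 35, a width of 5 − *t*.
- Mean width over 0–4 years: 5 − 2 = 3.
- Share of person-time: 3/19 = 15.8%.
- Share of the person-time at ages 30–34: 3/5 = 60%.
- With a one-year intervention the mean width is 4.5 and the share 4.5/19 = 23.7%, so four years gives the lowest share.

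**Step 3, dilution.** Apparent reduction = true reduction × (1 − *w*), where *w* is the never-eligible share of control-arm cases. With a flat rate *w* = 3/19, so 35% × 16/19 = 29.5%, and a rate ratio of 0.65 appears as 0.705.

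**Step 4, if PID is rarer in the never-eligible women.** With relative rate *r*, *w* = 3*r*/(3*r* + 16).

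| Relative rate *r* | *w* | Apparent reduction |
|---|---|---|
| 1 | 0.158 | 29.5% |
| 0.5 | 1.5/17.5 = 0.086 | 32.0% |
| 0.25 | 0.75/16.75 = 0.045 | 33.4% |

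**Step 5, information.** To first order, and counting Poisson variation only, information on the effect is cases × (effect)². All women give *N*(1 − *w*)²; ever-eligible women give *N*(1 − *w*). The ratio is 1/(1 − *w*) = 19/16 = 1.19 at a flat rate, 1.09 at *r* = 0.5 and 1.05 at *r* = 0.25.

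**Step 6, if older women benefit indirectly.** Suppose, for illustration, that they get half the effect. At a flat rate the apparent reduction is 35% × (16 + 1.5)/19 = 32.2%. The information ratio is (16/19)/(17.5/19)² = 0.99, so the gain in precision disappears.

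**The case against.** **The age range is explained, and a plain age band is simple.** True, and the limit fits the follow-up period. But the explanation covers women who age past 29, and not those who began past it.

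**Older women may benefit.** The Protocol says screening also prevents complications by lowering exposure, and it justifies randomising areas partly by shared sexual networks. Zero effect in women aged 30–34 is therefore the worst case. This stands. It shrinks the dilution, can remove the precision gain, and is a good reason to keep the all-women analysis.

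**Results by age group are already planned.** This helps only in part. A 30–34 band mixes women who aged out of eligibility with women never eligible, and a 16–29 band loses the late PID that the extension is meant to catch.

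**Two stronger readings are tempting and not supported.** A reader might infer from the data list that cases to age 34 will be divided by a 16–29 denominator, overstating incidence by up to 19/14 − 1 = 36%. The endpoint section fixes the denominator at 16–34. The listed item counts consultations rather than women, and the list is not stated to be complete. It is an omission from a list, not a planned miscalculation. A reader might also take the headcount share, 5 of 23 single-year start ages (12–34), or 22%, and conclude that 35% would shrink to about 27%. Women aged 30–34 at the start leave the age band during follow-up and contribute less time, so at a flat rate the case share is the person-time share, about 16%.

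**Conclusion.** The mismatch is in the text: objective and target at 16–29, endpoint at 16–34, and a reason that does not reach women already 30–34 at the start. The expected direction of the effect is toward no difference, so it would not create a false benefit.

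The size is modest and cannot be fixed from the Protocol, which gives no PID incidence at 30–34. Under even ages and attendance, four years, a flat rate and no indirect benefit, the never-eligible women supply about 16% of person-time and cases. A 35% reduction then appears as 29–30%, and restriction raises information by about 19%. If PID in these women is half to a quarter as common, the apparent reduction is about 32–33%. Indirect benefit reduces the loss further. The case for change therefore rests first on matching the objective, and only second on precision. For a secondary endpoint it is worth correcting because the change is small.

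**What to change.** 1. **Lead PID analysis:** women with at least one consultation while aged 16–29 during the intervention period. Count PID diagnosed at or after the first such consultation, up to age 34, so that PID diagnosed at that first visit is kept. The denominator is the same women.
2. **Supportive analysis:** all women aged 16–34, as now defined. Use this for sources without patient-level linkage: the backup pathology and Medicare data, which carry no unique patient code, and the State hospital data, for which no link to clinic consultations is described.
3. **Align the text:** use one population in the Secondary objectives, the PID endpoint and the data-collection section. Add the number of women in the PID denominator, to age 34, to the data list.

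**Cost:** wording changes and an age condition in the extraction query. The lead analysis has slightly fewer PID cases. It also leaves out women who were under 30 at the start but first attended after turning 30. It needs patient-level extraction, which exists only at clinics where the tool is installed.
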